1.0 BACKGROUND AND RATIONALE

1.1 Study Synopsis

Increasing the sensitivity and specificity of diagnostic imaging in patients at high risk for breast cancer could provide substantial clinical benefit by improving diagnosis, preventing over-treatment, and reducing healthcare costs. Acoustic angiography is a new type of contrast enhanced ultrasound imaging which is specifically sensitive to microvascular structure and density. It evaluates tumor micro-vasculature and may provide a powerful prognostic tool for the diagnosis of breast cancer, and eventually for treatment evaluation.

Sixty patients who are to have a clinical surgical breast biopsy based on results from pre-study standard of care (SOC) imaging will be recruited from the UNC Breast Clinic for participation in the study. The primary objective of this single arm study is to compare the sensitivity and specificity of acoustic angiography with traditional b-mode ultrasound in the distinction of malignant versus benign breast lesions. Secondary objectives include a comparison of area under the curve (AUC) for acoustic angiography versus b-mode ultrasound, and comparison of radiologist preference for the two imaging techniques for each of 3 lesion characteristics.

1.2 Traditional Breast Cancer Screening and Diagnosis

Breast cancer is the most common cancer type among women. Approximately 10% of women in the United States develop breast cancer during their lifetime and 30% to 40% of these patients will die from it.[33, 34] Mammography is an effective tool for the early detection of breast cancer in the majority of women.[35] However, for women with dense breast tissue (considered an independent risk factor for breast cancer) and younger women, mammography performs poorly due to lower sensitivity and specificity in these groups.[37] For young women with heritable mutations who wish to begin screening at a younger age, these limitations are especially problematic.[38] Additionally, mammography is less sensitive in women who have undergone breast augmentation. Given these limitations, most of these women may undergo additional imaging with breast ultrasound or Magnetic Resonance Imaging (MRI).

MRI is time consuming, extraordinarily costly, and has limited availability, especially among rural and underserved populations. Another screening option, breast ultrasound (without contrast), is widely used when additional imaging beyond mammogram is required due to its real-time imaging capability (>30 images per second), portability, safety (does not involve radiation), and relatively low cost compared to breast MRI. Unfortunately, while breast ultrasound is highly sensitive (96%), it is less specific (70%),

resulting in a high false positive rate. This results in unnecessary biopsies with associated complications, additional follow-up and negative psychosocial impacts on patients, e.g., significant anxiety. A significant clinical need exists to improve breast ultrasound sensitivity and specificity.

1.3 Angiogenesis

Angiogenesis is the development of new microvasculature, and is well recognized to be involved in the growth of solid tumors as well as tumor invasion and metastasis. Recent studies have reported an association between microvessel density and poorer recurrence-free, cancer-specific and overall survival.[39-46]. Furthermore, both microvessel density and microvessel morphology have been reported to be associated with the clinical response to chemotherapy.[16, 47-49] However, no current clinical imaging modality can directly evaluate the microvasculature associated with suspected breast tumors.[50] Histological techniques based on core needle biopsy or surgical biopsy may evaluate only a small portion of a lesion, and require additional invasive procedures. Thus, direct non-invasive evaluation of the tumor micro-vasculature may provide a powerful prognostic tool for the diagnosis of breast cancer, and also provide a potential tool for treatment evaluation.

1.3.1 Screening Based on Angiogenesis-Acoustic Angiography

Acoustic angiography allows for the viewing of vessel shape and delineation of 'tortuosity,' which can indicate the presence and progression of cancer. This ability to image the microvasculature depends on the use of a multi (high) frequency ultrasound scanner in addition to a traditional single-frequency pulse-echo ultrasound scanner (b-mode ultrasound), the latter to ensure accurate anatomical location of the lesion. Because of this dependence on pulse-echo, the technique is referred to as "acoustic" angiography [62].

Acoustic angiography also depends on use of an ultrasound contrast agent. Contrast enhanced ultrasound imaging has been used for nearly two decades for clinical cardiology in the United States (and is currently routinely used in UNC Hospital Cardiology Clinics), and is much more widely used in Europe and Asia for visualization of blood perfusion in organs, tissues, and tumors.[51] Early concerns about the safety of ultrasound contrast (specifically with the contrast agent (perflutren lipid; Definity®) due to events in a clinical trial have been resolved; the overwhelming amount of more recent evidence from large clinical studies has shown that contrast ultrasound is very safe.[52-54] In fact ,it is much safer than other commonly used techniques, such as coronary angiography, exercise ECG, or myocardial scintigraphy.[55] Furthermore, it does not have the risks of nephrogenic systemic fibrosis associated with gadolinium based MRI contrast agents when used in renally compromised patients. On October 27, 2011, the FDA eliminated the requirement for

patient monitoring 30 minutes after ultrasound contrast examination, based on these and other recent safety data. The ultrasound contrast agent to be used in LCCC1748 is perflutren lipid. An IND exemption will be requested from the FDA for the usage of perflutren prior to usage in this study.

1.4 Perflutren Lipid Background and Known Toxicities

See http://www.definityimaging.com/pdf/DEFINITY_US_PI_515987-0117.pdf for full prescribing information on perflutren when used according to its FDA-approved indication. Also see section 6.1.5.

1.4.1 Background and Current Indications

Definity® (perflutren lipid) is an FDA-approved lipid-shell microbubble ultrasound (US) contrast agent that may be administered by an intravenous (IV) bolus or infusion. Currently, this contrast agent is approved for use in patients with suboptimal echocardiograms to opacify the left ventricular chamber and to improve delineation of the left ventricular endocardial border. It is not approved as a contrast agent for acoustic angiography in the breast.

When used according to its approved indication, the maximum dose of perflutren is administered as either two bolus doses or one single intravenous infusion.

For our study, perflutren lipid will be administered intravenously by a nurse or trained medical personnel (see section 4.3).

1.4.2 Associated Toxicities

In pre-market clinical trials 1716 subjects were evaluated with activated perflutren lipid. Of the 1716 subjects, 144 subjects (8.4%) had at least one treatment-related adverse reaction. There were 26 serious adverse events and 15 (0.9%) subjects discontinued because of an adverse event.

Nineteen subjects (1.1%) suffered serious cardiopulmonary adverse events including eight deaths. The deaths occurred several days after activated perflutren lipid administration and appear to be related to the course of underlying disease. Of the 11 other serious adverse events, which appeared within 2-15 days of the drug administration, all appeared to be a progression of underlying cardiac and non-cardiac disease.

However, a role for perflutren lipid in the initiation or course of these adverse events cannot be ruled out.

There were 15 discontinuations reported. Nine of these patients were discontinued after the first injection. One patient experienced a hypersensitivity reaction with urticaria and pruritus and all the other patients experienced dizziness, chest pain, dyspnea or back pain. Adverse events (AEs) appeared within 1 – 15 minutes of the drug

administration and were of moderate intensity resolving usually without treatment within minutes or hours after onset.

For all AEs, there were no differences in the overall incidence based on age, gender, or route of administration. The most common events were (% of patients experiencing): headache (2.3%), back and renal pain (1.2%), flushing (1.1%) and nausea (1.0%).

Cardiopulmonary Reactions

In 2007, in response to post-marketing reports of 4 deaths and 190 serious cardiopulmonary reactions, the FDA issued a black box warning for both Definity® and Optison® adding disease state contraindications and a mandatory 30 minute monitoring period following administration in all patients. Following this there have been several large scale safety studies looking into the records of a total of more than 200,000 patients who received one of these contrast agents. In all those studies a composite rate of serious adverse events was calculated to be 1 – 3 in 10,000,[22] compared to gadolinium-based MRI contrast which has an incidence of NSF of 2 – 5 in 100 patients with chronic kidney disease.[23]

Following a meeting of the FDA Cardio-renal Advisory Committee in 2008, the black box warning was revised. The revisions shortened the contraindications to include cardiac shunts and hypersensitivity to perflutren, and mandated the 30 minute monitoring period be limited to patients with pulmonary hypertension or unstable cardiopulmonary conditions. The black box warning was further revised in 2011, removing the mandatory 30 minute monitoring period, but stating that most serious cardiopulmonary reactions occur within 30 minutes of administration. For this reason, the label states that cardiopulmonary resuscitation personnel and equipment be readily available prior to perflutren administration, and that all patients be monitored for acute reactions.

Patients with a history of cardiac shunts, pulmonary hypertension or unstable cardiopulmonary conditions will be excluded from our study. In addition, all patients will be monitored for 30-minute post-perflutren administration by the research nurse or research physician.

Hypersensitivity Reactions

The real risk of perflutren in our study is to the small number of potential patients with undiagnosed allergy to perflutren. Post-marketing reports have included anaphylactoid events and other serious but non-fatal adverse reactions, typically within 30 minutes of drug administration (see the package insert, and section 6.1.5 for additional information. In order to avoid a potentially fatal event, EpiPen® (epinephrine) injections will be kept near the US machine for all patients.

High Ultrasound Mechanical Index (MI)

High ultrasound MI values may cause microsphere cavitation or rupture and lead to ventricular arrhythmias. In addition, end-systolic triggering with high mechanical indices has been reported to cause ventricular arrhythmias.

Use in Patients with Known Breast Lesions

US contrast agents including perflutren should carry no additional risks in patients with a known breast lesions, as they are cleared by the lungs.

The phospholipid component of perflutren lipid microspheres are thought to be metabolized to free fatty acids, while the octafluoropropane (OFP), as a stable gas, is not metabolized. In a small (n=8) pharmacokinetic study in healthy subjects, OFP was undetectable after 10 minutes in most subjects either in the blood or expired air, with a mean half-life of 1.3 minutes (Definity® Prescribing Information) .

1.5 Rationale

One main limitation to the widespread use of contrast enhanced ultrasound clinically has been the lack of availability of state-of-the art contrast imaging approaches available to clinicians. However, contrast ultrasound will likely become far more widespread as new imaging techniques, such as acoustic angiography, demonstrate their usefulness and become available on commercial ultrasound systems. We propose to evaluate a novel ultrasound method that could potentially improve the sensitivity and specificity of traditional breast ultrasound. Increasing the accuracy of diagnostic imaging in high risk patients could provide substantial clinical benefit by improving diagnosis, preventing over-treatment, and reducing healthcare costs.

LCCC1748 is designed to compare the sensitivity and specificity of contrast enhanced ultrasound (acoustic angiography) to the sensitivity and specificity of conventional ultrasound in women scheduled to undergo a biopsy based on pre-study imaging results. The gold standard for sensitivity and specificity, then, will be based on pathological results. The Breast Imaging Reporting and Data System (BIRADS) is used by radiologists who read mammograms, ultrasounds and MRIs to indicate their level of suspicion of the possibility of breast cancer. Scores range from 0 to 6, with scores of 4-5 indicating suspicious results, while 6 indicates an existing diagnosis of breast cancer. This study is limited to women with a score of 4-5 based on pre-study imaging.

2.0 STUDY OBJECTIVES AND ENDPOINTS

2.1 Primary Objective

To compare (using a reader study) the sensitivity and specificity of acoustic angiography to the sensitivity and specificity of conventional b-mode ultrasound in evaluation of known breast lesions for predicting malignancy.

2.2 Secondary Objectives

- 2.2.1 To compare the area under the curve (AUC) of acoustic angiography to the AUC of the b-mode ultrasound
- 2.2.2 To compare radiologist preference of acoustic angiography to conventional b-mode ultrasound for each lesion characteristic (shape, margins, and vascularity)

2.3 Primary Endpoint

Sensitivity and specificity for our study is defined as the ability of readers (radiologists) to use the acoustic angiography or b-mode ultrasound to distinguish between malignant and non-malignant breast lesions known to exist based on pathological results (the gold standard).

3.0 ELIGIBILITY

3.1 Inclusion Criteria

Subject must meet all of the inclusion criteria to participate in this study:

- 3.1.1 Women \geq 18 years old
- 3.1.2 Patient had a diagnostic breast ultrasound study performed at UNC
- 3.1.3 Scheduled for a core needle or surgical breast biopsy of at least one breast lesion that is 2 cm or less in size and 3 cm in depth from the skin surface
- 3.1.4 Lesion visualized on ultrasound
- 3.1.5 Able to provide informed consent
- 3.1.6 Negative urine pregnancy test in women of child-bearing potential

3.2 Exclusion Criteria

All subjects meeting any of the exclusion criteria at baseline will be excluded from study participation

3.2.1 Male (it is uncommon for men to present for imaging and the overwhelming majority of findings are non-cancerous and do not lead to biopsy; male breast cancer represents <1% of newly diagnosed breast cancer)

3.2.2 Institutionalized subject (prisoner or nursing home patient)

3.2.3 Critically ill or medically unstable and whose critical course during the observation period would be unpredictable (e.g., chronic obstructive pulmonary disease (COPD))

3.2.4 Sonographically visible breast lesion larger than 2cm or greater than 3cm in depth from the skin surface

3.2.5 Known hypersensitivity to sulfur hexafluoride or to any component of perflutren lipid (Definity®)

3.2.6 Active cardiac disease including any of the following:

[figure not shown]
- Severe congestive heart failure (class IV in accordance with the classification of the New York Heart Association)
- Unstable angina.
- Severe arrhythmia (i.e. ventricular tachycardia, flutter fibrillation; ventricular premature complexes occurring close to the preceding T-wave, multifocal complexes).
- Myocardial infarction within 14 days prior to the date of proposed Definity® administration.
- Uncontrolled systemic hypertension (systolic blood pressure (BP) >150 mm Hg and/or diastolic BP >90 mm Hg despite optimal medical management).

3.2.7 Any woman who is pregnant or has reason to believe she is pregnant or any woman who is lactating (the possibility of pregnancy has to be excluded by negative urine β -HCG results, obtained within 24 hours before the perflutren lipid administration, or on the basis of patient history, as defined by the UNC IRB SOP 4801.)

4.0 **STUDY PLAN**

4.1 **Schema**

This is a one arm single center study of 60 patients scheduled to be biopsied from the UNC Breast Clinic that consent to undergo an acoustic angiography in conjunction with b-mode ultrasound prior to their scheduled biopsy.

¹Pre-ultrasound contrast agent

²Based on results of pre-study imaging

4.2 Enrollment/Recruitment

A total of 60 women will be enrolled to this study. The 60 study subjects will be consecutively recruited from women who are scheduled to undergo core needle or surgical biopsy to have pathological confirmation of malignancy status. Eligible patients will be identified by research staff review in coordination with the UNC Breast Clinic.

Once a patient has been referred, the patient will be approached by a coordinator from Radiology to assess interest in participation.

All eligible women who agree to participate in the study will be asked to come to their scheduled biopsy appointment thirty minutes early to complete the informed consent process.

Review of the consent will take place in the privacy of an exam room, or when possible, a sample consent form will be sent to the patient via email prior to the patient's visit to allow for ample review. Once the patient has consented, women of child bearing potential (WCBP) will be given a urine pregnancy test in order to ensure that they are not pregnant. If a urine pregnancy test shows a result positive for pregnancy, the patient will be excluded from the study per the exclusion criteria because the investigators cannot, in good conscience, expose a fetus to the contrast agent used. Women who consent for the study and are eligible will be escorted by the research coordinator to a dressing room, where the subject will change into a gown.

4.3 Acoustic Angiography

4.3.1 Perflutren Administration

At the time of imaging, the contrast agent perflutren lipid (see section 4.3) will be administered. See http://www.definityimaging.com/pdf/VIALMIX_Users_Guide.pdf, and the package insert, for instructions on perflutren lipid preparation and activation. Perflutren lipid is intended for intravenous (IV) administration only after activation in the Vialmix® apparatus. Cardiopulmonary resuscitation personnel and equipment will be readily available prior to

perflutren administration, and all patients will be monitored for acute reactions.

Perflutren will be administered in split doses using the dosing range and administration type IV bolus) within the perflutren prescribing information (see <http://www.definityimaging.com/how-administration.html>). When administered as a bolus, the package insert recommends 10 uL/kg patient weight administered within 30-60 seconds, followed by a 10mL saline flush with a second dose of 10 uL/kg patient weight 30 minutes following the first dose, if needed. All patients will be monitored for 15-minute post-perflutren administration by the research nurse or research physician. Monitoring will include taking vitals (O₂ sat, HR, RR, BP). The oxygen saturation, heart rate, and respiration rate will be monitored continuously for 15 min. The blood pressure will be monitored at 15 minutes. This study will be conducted in Mammography of the UNC Cancer Hospital, so trained medical personnel will be available as needed.

We will infuse via hand bolus injection for a "precision controlled bolus".

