6.1.5 Clinical Safety Summary

See prescribing information on perflutren when used according to its FDA indication (http://www.definityimaging.com/pdf/DEFINITY_US_PI_515987-0117.pdf), and see section 1.3 for a summary of toxicities reported in clinical trials. In addition, the following warnings and precautions are noted in the January 2017 labeling:

Serious Cardiopulmonary Reactions:

Serious cardiopulmonary reactions including fatalities have occurred uncommonly during or shortly following perflutren-containing microsphere administration, typically within 30 minutes of administration. The risk for these reactions may be increased among patients with unstable cardiopulmonary conditions (acute myocardial infarction, acute coronary artery syndromes, worsening or unstable congestive heart failure, or serious ventricular arrhythmias). Always have cardiopulmonary resuscitation personnel and equipment readily available prior to DEFINITY administration and monitor all patients for acute reactions. The reported reactions include: fatal cardiac or respiratory arrest, shock, syncope,

symptomatic arrhythmias (atrial fibrillation, tachycardia, bradycardia, supraventricular tachycardia, ventricular fibrillation, ventricular tachycardia), hypertension, hypotension, dyspnea, hypoxia, chest pain, respiratory distress, stridor, wheezing, loss of consciousness, and convulsions. *Hypersensitivity Reactions:*

In postmarketing use, serious hypersensitivity reactions were observed during or shortly following perflutren-containing microsphere administration including: Shock, bronchospasm, throat tightness, angioedema, edema (pharyngeal, palatal, mouth, peripheral, localized), swelling (face, eye, lip, tongue, upper airway), facial hypoesthesia, rash, urticaria, pruritus, flushing, and erythema have occurred in patients with no prior exposure to perflutren-containing microsphere products. Always have cardiopulmonary resuscitation personnel and equipment readily available prior to DEFINITY administration and monitor all patients for hypersensitivity reactions.

Systemic Embolization of Perflutren in Patients with Cardiac Shunts:

When administering DEFINITY to patients with a cardiac shunt, the microspheres can bypass filtering by the lung and enter the arterial circulation. Assess patients with shunts for embolic phenomena following DEFINITY administration. DEFINITY is only for intravenous administration; do not administer DEFINITY by intra-arterial injection.

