11.5 Adherence to the Protocol

Except for an emergency situation in which proper care for the protection, safety, and well-being of the study patient requires alternative treatment, the study shall be conducted exactly as described in the approved protocol.

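### Section 1.4.2 commits to 30 minutes of post-contrast monitoring for every patient, but the procedure in section 4.3.1 specifies 15

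*Combined protocol and SAP*

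**What the plan says.** The discussion of cardiopulmonary reactions in section 1.4.2 ends with a commitment that "all patients will be monitored for 30-minute post-perflutren administration by the research nurse or research physician". The procedure for giving the agent, in section 4.3.1, instead states: "All patients will be monitored for 15-minute post-perflutren administration by the research nurse or research physician". It then fixes the measurements to the shorter period: "The oxygen saturation, heart rate, and respiration rate will be monitored continuously for 15 min. The blood pressure will be monitored at 15 minutes".

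The protocol also says when reactions are expected. Section 1.4.2 describes the 2011 label revision as "removing the mandatory 30 minute monitoring period, but stating that most serious cardiopulmonary reactions occur within 30 minutes of administration". Under hypersensitivity it adds: "Post-marketing reports have included anaphylactoid events and other serious but non-fatal adverse reactions, typically within 30 minutes of drug administration". The labeling warnings reproduced in section 6.1.5 place serious cardiopulmonary reactions "typically within 30 minutes of administration".

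Section 4.3.1 contains two further safeguards with no stated duration: monitoring of all patients for acute reactions, and trained medical staff available if needed. Section 11.5 requires, outside emergencies, that "the study shall be conducted exactly as described in the approved protocol".

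**The concern.** Two current instructions on one safety procedure disagree by a factor of two. Section 4.3.1 is where staff will look when giving the agent. It states 15 minutes three times: for monitoring overall, for oxygen saturation, heart rate and respiration, and for blood pressure. A single typing slip is therefore an unlikely explanation, and staff who follow that section will stop at 15 minutes.

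The protocol's own account of risk points to the longer period. It puts most serious cardiopulmonary reactions, and typically the post-marketing anaphylactoid and other serious ones, within 30 minutes. It also says that "The real risk of perflutren in our study is to the small number of potential patients with undiagnosed allergy to perflutren", and such patients cannot be screened out in advance. Imaging is estimated at under 15 minutes (section 4.3.2) and the biopsy follows (section 4.4). A patient could thus go into biopsy inside the cited window with no vital signs required by the protocol.

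There is a compliance consequence too. Stopping at 15 minutes satisfies section 4.3.1 and departs from section 1.4.2. Section 11.5.3 separates deviations from violations partly by their effect on participant risk, so the site would have to classify such departures without a settled standard.

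**Working it through.** The protocol gives no calculated figure to reproduce here. The check is a comparison of text, followed by simple arithmetic on size and cost.

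**1. The two instructions side by side**

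- Population: all patients in both sections.
- Staff: a research nurse or physician in both.
- Starting event: perflutren administration in both.
- Duration: 30 minutes in section 1.4.2; 15 minutes in section 4.3.1.

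**2. Readings that might reconcile them**

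- *30 minutes is only for high-risk patients.* The sentence in 1.4.2 covers everyone and directly follows a statement that such patients are excluded.
- *30 minutes describes the label.* The same section reports that the label's mandatory period was removed in 2011 and then commits this study to 30 minutes. It is the study's own undertaking.
- *15 minutes per dose adds up to 30.* Section 4.3.1 mentions split doses, but nothing says that the periods apply per dose or are summed.
- *15 minutes is for vital signs, 30 for looser observation.* Section 4.3.1 applies 15 minutes to the general monitoring sentence as well as to the measurements.

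None of these works. Monitoring for 30 minutes satisfies both sections; stopping at 15 does not.

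**3. Size of the gap in time**

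30 − 15 = 15 minutes per patient, and 15/30 = one half of the cited window. This is a share of time, not of risk.

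**4. Absolute risk**

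Inputs: n = 60 patients (section 4.2), and a composite serious-event rate p of 1 to 3 per 10,000 from the large safety studies summarised in section 1.4.2. Assumption: that rate applies to these patients.

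- Expected serious events, n × p: 60 × 0.0001 = 0.006, to 60 × 0.0003 = 0.018.
- Chance of at least one, 1 − (1 − p)^n: 1 − 0.9999^60 = 0.0060, to 1 − 0.9997^60 = 0.0178.

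The chance over the whole study is therefore about 0.6% to 1.8%. The documents do not give the share of reactions that start between 15 and 30 minutes. If it can be anything from 0 to 1, the chance of a serious reaction starting in those minutes lies between 0% and 1.8%. The top of that range needs the highest rate and every reaction starting in that quarter-hour, which nothing in the documents supports. It is a ceiling, not an estimate.

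**5. Extra observation if monitoring runs to 30 minutes after the last dose**

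Section 4.3.1 does not say which dose starts its clock. It cites package-insert advice that a second bolus, if needed, follows 30 minutes after the first.

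- Clock already starts at the last dose: 30 − 15 = 15 more minutes per patient, and 60 × 15 = 900 minutes = 15 hours.
- Clock starts at the first dose and a second follows at 30 minutes: monitoring would end at 30 + 30 = 60 minutes instead of 15, which is 60 − 15 = 45 more minutes for that patient.

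**The case against.** The best defence is that patients are not left unwatched. Besides the untimed monitoring and available staff in section 4.3.1, resuscitation personnel and equipment must be ready beforehand, and section 1.4.2 keeps epinephrine near the machine. The patient then goes on to her biopsy rather than home. This stands as a limit on the point. What ends at 15 minutes is the specified monitoring by the nurse or physician with vital signs; observation of any kind need not end. But untimed monitoring sets no duration or measurements, so it does not deliver the 30 minutes promised in section 1.4.2.

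Some protocol text also favours a shorter period. In the section 1.4.2 paragraph on discontinuations, adverse events appeared within 1 to 15 minutes. In a study of eight healthy subjects the gas was undetectable after 10 minutes in most. Those adverse events were of moderate intensity, however, and the protocol uses neither observation to justify 15 minutes.

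A reader might infer that 15 minutes breaches the product label. The documents do not support that: as the protocol describes it, the mandatory 30-minute period was removed in 2011.

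**Conclusion.** The inconsistency is real and cannot be resolved from the protocol text. It is a moderate safety inconsistency. It touches all 60 patients and leaves the second half of the cited 30-minute window without the specified vital signs if section 4.3.1 is followed. The expected number of serious events is small, 0.006 to 0.018 over the study, on the assumption that the quoted rate carries over. How much of that risk falls between 15 and 30 minutes is unknown.

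A reader might also infer that the trial should not proceed until this is corrected, or that its results are compromised. Neither follows. Staff can comply with both sections now by monitoring for 30 minutes, emergency cover is in place, and the sample size, power and sensitivity and specificity analyses do not depend on the monitoring period. The case for correction is that a safety procedure should carry one duration, and that 30 minutes is the one matching the protocol's commitment and stated rationale. The conclusion rests on the protocol text alone; the consent form was not available for comparison.

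**What to change.** Amend section 4.3.1 to require 30 minutes of monitoring by the research nurse or physician after the last perflutren dose, with oxygen saturation, heart rate and respiration followed continuously to 30 minutes. Keep the blood pressure reading at 15 minutes and add a second at 30. Moving the existing reading would remove the only specified early check, in the period when the adverse events described with the discontinuations appeared. Naming the last dose also settles when the clock starts, which neither section does now.

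The cost is a wording amendment plus observation time from staff already assigned: about 15 minutes per patient, or 15 staff-hours in all, if the present clock runs from the last dose. If it runs from the first, a patient given a second dose 30 minutes later would need up to 45 more minutes. The biopsy may start correspondingly later. If the sponsor prefers 15 minutes, section 1.4.2 must be changed to match and the shorter period justified against the 30-minute window cited there and in section 6.1.5.

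### In the readable text no vital sign is scheduled before contrast, so the one post-contrast blood pressure has no study baseline

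*Combined protocol and SAP*

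**What the plan says.** Section 3.2 sets the time at which exclusions apply: "All subjects meeting any of the exclusion criteria at baseline will be excluded from study participation". Within 3.2.6, under active cardiac disease, one item is "Uncontrolled systemic hypertension (systolic blood pressure (BP) >150 mm Hg and/or diastolic BP >90 mm Hg despite optimal medical management".

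Section 4.2 describes how women reach the scanner. "Eligible patients will be identified by research staff review in coordination with the UNC Breast Clinic". Consent follows, then "women of child bearing potential (WCBP) will be given a urine pregnancy test in order to ensure that they are not pregnant", then changing into a gown. No blood pressure, heart rate, respiration rate or oxygen saturation is mentioned.

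Section 4.3.1 names four vitals (oxygen saturation, heart rate, respiration rate, blood pressure) as part of monitoring after the injection: "All patients will be monitored for 15-minute post-perflutren administration by the research nurse or research physician". It then gives the timing: "The oxygen saturation, heart rate, and respiration rate will be monitored continuously for 15 min", and "The blood pressure will be monitored at 15 minutes".

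Section 6.1.5 lists the reported serious cardiopulmonary reactions, which include "hypertension, hypotension, dyspnea, hypoxia, chest pain, respiratory distress". Section 1.4.2 states a 30-minute monitoring period for all patients, not 15.

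**The concern.** A single blood pressure taken after an exposure shows the level but not the change. If the value at 15 minutes is high or low, the study data cannot show whether it moved after contrast or was already there in a woman waiting for a breast biopsy. Section 7.2 asks for the severity of each event and its relationship to the drug, and two of the reactions in 6.1.5 are defined by blood pressure.

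There is a second, smaller matter. The exclusion in 3.2.6 carries a numeric limit, but the protocol does not say which reading it is judged on. Section 11.5.2 allows no eligibility exceptions, so it should be possible to verify afterwards that a numeric criterion was met.

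**Working it through.** The plan gives no figure to reproduce. The check is a reading of the visit in order, counting scheduled vital signs.

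| Step | Section | Vital sign scheduled |
|---|---|---|
| Identification by staff review | 4.2 | none |
| Consent | 4.2 | none |
| Urine pregnancy test | 4.2 | none |
| Gown | 4.2 | none |
| Conventional ultrasound for localization | 4.3.2 | none |
| Perflutren bolus | 4.3.1 | none stated before injection |
| Monitoring after perflutren | 4.3.1 | oxygen saturation, heart rate, respiration rate continuously for 15 minutes; blood pressure at 15 minutes |
| Biopsy | 4.4 | none |
| Record abstraction | 4.5 | none; the pathology report is the item named |

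**Count.** Pre-contrast vital-sign readings scheduled: 0. Blood-pressure time points scheduled: 1 per monitoring period. A change score needs one value before and one after, so the scheduled study data give a blood-pressure change for 0 of 60 women.

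**The other three vitals.** A continuous trace shows movement within the 15 minutes, so a fall in saturation or a run of fast or slow heart rate can be seen against the rest of the same trace. What is missing is the level before injection.

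**Source for the 3.2.6 limit.** Compare the neighbouring criterion. Section 3.2.7 names the evidence for pregnancy status (a urine test), its window (within 24 hours before perflutren) and an alternative (patient history), and 4.2 schedules the test. The blood-pressure item has a number but no source, date window or number of readings.

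**Monitoring passages.** Section 1.4.2 gives 30 minutes and section 4.3.1 gives 15, a difference of 30 − 15 = 15 minutes. Section 4.3.1 also refers to split doses and does not say from which dose the 15 minutes run, so the time of the one blood pressure is itself not fully fixed.

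**Limit of the check.** The schema in 4.1 is not shown. One of its footnotes marks some step as coming before the contrast agent, and that step cannot be identified. Nothing in 4.2 to 4.4 suggests that it is a vital-sign reading, but the absence is established for the readable text only.

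**The case against.** The strongest reply is about eligibility. A reader might infer that women are exposed before the measurement that should exclude them is taken, so that anyone above 150/90 on the day would receive contrast. The documents do not support this. The criterion describes hypertension that stays uncontrolled under optimal treatment, which is an established clinical status. Its companion items, such as class IV heart failure or unstable angina, have no scheduled study test either. Staff review with the clinic can draw on existing readings, and no same-day limit is stated. This part of the reply stands; what remains is that the source and date window are not named.

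A reader might also cite the onset of 1 to 15 minutes in section 1.4.2 as evidence that falls in blood pressure will be missed. The discontinuation events described there are a hypersensitivity reaction with urticaria and pruritus, and otherwise dizziness, chest pain, dyspnea or back pain. No blood-pressure change is reported among them. A change that resolves before 15 minutes would not be captured by the one reading, but that passage does not show that such changes occur.

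Nor does section 7.1.2 require a pre-dose measurement. It lists temporal relationship as one of several factors in judging causality. A baseline would help that judgment but is not a condition for it.

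Finally, vital signs are not an endpoint and no analysis in section 10.2 uses them. Patients are attended throughout monitoring, and routine pre-biopsy vitals may be taken in practice. These points limit the consequence. They do not supply the comparator, because the protocol does not say that any such reading is taken or recorded for the study.

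**Conclusion.** The point holds as a gap in safety data. As written, the study schedules no pre-contrast vital sign and one post-contrast blood pressure, so for all 60 women a reported rise or fall in blood pressure has no study baseline. The gap is smaller for the three continuously monitored vitals. The unnamed source for the 3.2.6 limit is a documentation gap; it is not evidence that ineligible women will be given contrast. The 30-minute and 15-minute monitoring statements contradict each other and must be reconciled.

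This rests on the readable text and would change if the schema shows a pre-contrast reading. It has no bearing on the sensitivity and specificity estimates or on the power calculation.

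**What to change.** 1. In 4.2 or 4.3.1, provide for one set of the four vitals already named, recorded on the CRF after consent and before perflutren, as the comparator for the post-contrast values.
2. State which blood-pressure source is used to judge 3.2.6 and the period it may come from, in the way 3.2.7 does for pregnancy status.
3. Reconcile the monitoring passages: the duration in 1.4.2 against 4.3.1, the single blood-pressure time point, and the dose from which the time is counted.

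The pre-contrast set is proposed as a comparator, not as a new eligibility check. Thresholds, eligibility decisions and clinical actions stay with the sponsor.

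The cost is assumed to be a few minutes and one CRF line per woman. The documents give no figure, but 4.3.1 already provides for the measurements and the monitoring staff.
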